GRANT APPLICABILITY:

Indicate whether this protocol is funded by a grant (e.g. NIH, foundation grant). For a grant with multiple aims, indicate which aims are covered by this research proposal.

NOTE: This question does not apply to studies funded by a sponsor contract.

Include a copy of the grant proposal with your submission.

Response: Potential funding from the 2021 CTSI Pilot Study

RESEARCH REPOSITORY:

Indicate where the research files will be kept, including when the study has been closed. The repository should include, at minimum, copies of IRB correspondence (approval, determination letters) as well as signed consent documents. This documentation should be maintained for 3 years after the study has been closed.

Response: Electronic research files will be kept in a dedicated Folder for this specific research project in UB Box, password protected according to the UB SON guidelines.

Location: UB BOX Research File

Address: [name]

Department: School of Nursing

1.0 Study Summary

| | |
|--------------------|--|
| Study Title | Piloting an evidence-based mobile mindfulness practice to support self-management among Underserved and Racial Minority Adults with Pulmonary Hypertension |
|--------------------|--|

| | |
|---|--|
| Study Design | two-group comparative study design where waitlisted participants will serve as controls. |
| Primary Objective | to determine the feasibility, acceptability, and preliminary impacts of the Mindfulness Meditation for PH (MMPH) mobile-health program in URM adults with PH in symptom management and quality-of-life |
| Secondary Objective(s) | None |
| Research Intervention(s)/ Investigational Agent(s) | Mindfulness Meditation for PH (MMPH) mobile-health program |
| IND/IDE # | None |
| Study Population | Community-dwelling URM adults diagnosed with PH condition |
| Sample Size | 20 |
| Study Duration for individual participants | 16 weeks (2 months) 18 participation (8 weeks for the intervention and eight weeks for follow up) |
| Study Specific Abbreviations/ Definitions | URM=underserved racial minority; PH=pulmonary hypertension; HRQOL=health-related quality of life; MMPH=mindfulness meditation for PH; GBM=gentle body movement; BAM=body awareness meditation; PAHSS=Pulmonary Arterial Hypertension Symptoms Scale; EmPHasis-10= Health-related quality of life in pulmonary arterial hypertension; PHQ-9=Patient Health Questionnaire; CAMS-R=Cognitive and Affective Mindfulness Scale-Revised; SUS= System Usability Scale |

2.0 Objectives*

2.1 *Describe the purpose, specific aims, or objectives of this research.*

Aim 1: To determine the feasibility and acceptability of the MMPH in community-dwelling URM adults with PH as a symptom self-management tool.

Aim 1a: Feasibility will be assessed by 1) frequency of home practice (> 2/week) and 2) retention rate (>70% of participants remaining at study completion).

Aim 1b: Acceptability will be determined by 1) participants' evaluation of the MMPH program (composite mean System Usability Scale score > 5, scale 1-7), 2) session completion rate (at least 6 of 8 [75% attendance] by the participants retained at the study end), and 3) qualitative thematic analysis of participants.

Aim 2: To determine the clinical impacts of an MMPH program in PH-symptom, anxiety, and depression reduction among community-dwelling URM adults with PH for symptom management.

2.2 *State the hypotheses to be tested, if applicable.*

NOTE: A hypothesis is a specific, testable prediction about what you expect to happen in your study that corresponds with your above listed objectives.

Hypothesis 1: MMPH will meet feasibility and acceptability targets for URM adults with PH

Hypothesis 2: Participants will report reductions in symptom severity of pain, anxiety, dyspnea, and fatigue at the end of the MMPH modules (short-term impacts). Participants will report decreases in the prevalence and intensity of PH-related symptoms, depression, and improved quality of life at the end of the MMPH program (long-term impacts).

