13.0 Study Timelines*

13.1 *Describe the anticipated duration needed to enroll all study subjects.*

As previously described, we anticipate enrolling all 20 subjects within three months.

13.2 *Describe the duration of an individual subject's participation in the study. Include the length of study visits and overall study follow-up time.*

The duration of an individual subject's participation in the entire study (consent to the completion of focused-group interview) will be three months or less. There will be no physical study visits, only virtual study visits for Zoom participation and individual interview sessions.

- Enrollment, consenting, baseline data = 30 minutes
- Completion of all 8 sessions (60 min/each) = 480 minutes for the 8 weeks
- 20min/day practice for 8 weeks = 56 days X 20 min = 1,120 min = 18.7 hours over 8 weeks = 2.3 hours per week.
- Focused interview = 1 hour
- Questionnaires completion = 10 min X 8 weeks = 80 min total

13.3 *Describe the estimated duration for the investigators to complete this study (i.e. all data is collected and all analyses have been completed).*

The estimated duration for the investigators to complete this study will be about 12 months (recruitment, enrollment, intervention, data collection, data analysis).

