21.0 Provisions to Monitor the Data to Ensure the Safety of Subjects*

N/A: This study is not enrolling subjects, or is limited to records review procedures only. This section does not apply.

NOTE: Minimal risk studies may be required to monitor subject safety if the research procedures include procedures that present unique risks to subjects that require monitoring. Some examples include: exercising to exertion, or instruments that elicit suicidality or substance abuse behavior. In such cases, N/A is not an acceptable response.

21.1 Describe the plan to periodically evaluate the data collected regarding both harms and benefits to determine whether subjects remain safe.

The PI will be responsible for safeguarding data integrity and safety monitoring for human subjects and communicating any negative outcomes or serious events to the IRB and other applicable offices/agencies.

The research team will meet weekly to review participant data and accrual. If participant accrual or retention drop under the requirement to complete the study, the PI and research team will discuss and develop strategies to overcome the identified issues. Record from the participants enrolled during each will be reviewed to ensure that all participants are eligible for the study. The research team will also monitor developments in the literature and results of related studies that may impact the participants or the ethics of the research.

21.2 Describe what data are reviewed, including safety data, untoward events, and efficacy data.

To ensure the integrity of the research study, we will review progress relevant to study recruitment and enrollment, intervention fidelity, clinical outcomes, and safety data. With the minimal to low risk associated with this research, there are no anticipated life-threatening adverse events for this proposed research project. In the rare occurrence, it will be reported to the PI and research team immediately. Researchers will notify the IRB within seven days of the adverse event occurrence. A thorough investigation will be initiated, including a review of the protocol to ensure no undue exposure to risk occurred.

21.3 Describe any safety endpoints.

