22.0 Withdrawal of Subjects*

N/A: This study is not enrolling subjects. This section does not apply.

22.1 Describe anticipated circumstances under which subjects may be withdrawn from the research without their consent.

Participants may be withdrawn from the research without their consent if the PI or research team member discovers a participant is in severe psychological distress or is admitted into the hospital for a psychiatric condition.

22.2 Describe any procedures for orderly termination.

NOTE: Examples may include return of study drug, exit interview with clinician. Include whether additional follow up is recommended for safety reasons for physical or emotional health.

NOT APPLICABLE

22.3 Describe procedures that will be followed when subjects withdraw from the research, including retention of already collected data, and partial withdrawal from procedures with continued data collection, as applicable.

We will attempt to use all the available data obtained from all participants (intention to treat). Pre and post comparison of the experimental Group will be conducted as aggregate means using all available data collected.

When participants decide to leave the study, we will ask them if they would allow us to use the data we have collected before their decision to withdraw. If the subjects agree to use the data, the collected data will be handled and analyzed the same as research data. If the participants do not allow the use of the data, we will make every attempt to destroy the data.

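### Session completion in Aim 1b is counted only among participants who stay to study end, so attendance among everyone offered the program can be overstated

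*Combined protocol and SAP*

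**What the plan says.** Section 2.1, Aim 1b, sets three acceptability measures. The second is "session completion rate (at least 6 of 8 [75% attendance] by the participants retained at the study end". Loss of participants is judged separately in Aim 1a, by "retention rate (>70% of participants remaining at study completion". Acceptability is part of the primary objective in Section 1.0, and Hypothesis 1 in Section 2.2 is that the feasibility and acceptability targets will be met.

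The analysis plan in Section 19.1 does not say how session completion is calculated. Section 22.3 has a general statement that available data from all participants will be used, labelled intention to treat. The sentence after it concerns a different quantity: "Pre and post comparison of the experimental Group will be conducted as aggregate means using all available data collected".

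The documents do not fix when the study ends for a participant. Section 1.0 gives "8 weeks for the intervention and eight weeks for follow up". Section 13.2 says participation ("consent to the completion of focused-group interview) will be three months or less"). Table 1 in Section 12.1 stops at week 8.

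**The concern.** Leaving an eight-week program early is itself evidence about how acceptable the program is. A completion rate restricted to those who stayed leaves that evidence out and describes a group selected partly by the behaviour being measured. Table 1 schedules the other two acceptability measures, the usability scale and the interview, only in the final week, so all three would describe mainly stayers. Session completion is the one measure that could include leavers without further contact, because sessions attended before leaving can be counted.

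At stake is whether one target under the primary objective is reported as met. Retention shows how many left, but not how many sessions they had attended.

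The rule is also open in two ways. It does not say whether 75% is mean attendance or a share of people, and it gives no share that must pass. And if study end includes follow-up, a person who finished all eight sessions and then left is excluded too, which pushes the error the other way.

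**Working it through.** **Inputs from the documents**
- 20 enrolled, 20% attrition, at least 16 remaining (Section 5.1). Section 7.3 uses 15% attrition instead.
- Eight sessions per person (Section 6.1), so 20 × 8 = 160 session slots.
- Completion threshold 6 of 8; retention target above 70% (Section 2.1).

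**Assumptions, because the documents give no figure**
- All 20 are offered MMPH.
- Leavers each attended k sessions, with k ranging from 0 to 8.

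**The plan's own figures reproduce.** 16 / (1 − 0.20) = 20, and 6 / 8 = 75%. Since 70% of 20 is 14, retention above 70% needs at least 15, so five people can be lost with the retention target still met.

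**Mean-attendance reading.** With r retained who attend exactly 6 sessions, the criterion as written reads 75%. Over all 20 the rate is (6r + (20 − r)k) / 160.

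| Sessions attended by leavers (k) | 16 retained | 15 retained |
|---|---|---|
| 0 | 96/160 = 60.0% | 90/160 = 56.3% |
| 5 | 116/160 = 72.5% | 115/160 = 71.9% |
| 6 | 120/160 = 75.0% | 120/160 = 75.0% |
| 8 | 128/160 = 80.0% | 130/160 = 81.3% |

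The gap is the share lost times (6 − k)/8. Each session of difference between stayers and leavers therefore moves the rate by 0.20/8 = 2.5 percentage points with 16 retained, or 0.25/8 = 3.1 points with 15.

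**Share-of-people reading.** Suppose every retained participant reaches 6 sessions and no leaver does. The rate as written is 100% in both cases.
- 16 retained: 16/20 = 80%, exact 95% confidence interval 56.3% to 94.3%.
- 15 retained: 15/20 = 75%, exact 95% confidence interval 50.9% to 91.3%.
- If 12 of 16 retained reach 6 sessions, 12/16 = 75% becomes 12/20 = 60%.
- If all leavers also reached 6 sessions, the first two cases become 20/20 and there is no gap.

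**If only one group is offered MMPH.** Section 5.1 describes a waitlist control with 8 to 10 per group, and no section says whether waitlisted participants later receive the program. With 10 offered, 8 retained and all 8 reaching 6 sessions, 100% becomes 8/10 = 80% if neither leaver did, with an exact 95% confidence interval of about 44% to 97%. The mechanism is the same and the precision is worse.

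**The case against.** The strongest reply is that this is an openly stated two-part definition. Dropout is judged in Aim 1a, completion among stayers in Aim 1b, and Hypothesis 1 needs both. On the share-of-people reading, if no leaver reached 6 sessions, multiplying the two rates gives the all-enrolled rate. That holds, but only under that condition. Otherwise the leavers' sessions are needed, and no section commits to reporting them.

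Section 19.1 promises frequency distributions for all variables, and Section 22.3 has its intention-to-treat statement. Attendance counts may well appear in the report. Neither text sets a denominator for this target, however, and if Section 22.3 is meant to cover it, it conflicts with Aim 1b and the two need reconciling.

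The direction of the error is not certain. This stands: the range over all 20 runs from 56.3% to 81.3% against 75% as written, the extremes are assumptions, and the confidence intervals are wider than the 20 to 25 point gap.

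Finally, this is a small pilot, no progression rule hangs on the rate, and Section 3.1 names only symptom severity and quality of life as scientific endpoints. That limits the consequences. But feasibility and acceptability head the primary objective, so their denominators matter.

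**Conclusion.** The concern holds. As written, the target excludes everyone who leaves, and nothing else in the plan supplies the rate over those offered MMPH. At the planned retention of 16 of 20, the figure can be too high by up to 15 points on the mean-attendance reading (75% against 60%) or 20 points on the share-of-people reading (100% against 80%). At 15 of 20, the limits are about 19 points (75% against 56.3%) and 25 points (100% against 75%). The error is nil if leavers attended as well as stayers. On the mean reading it reverses by 5 to 6 points if leavers completed all eight sessions and left in follow-up.

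These sizes assume that all 20 are offered MMPH and that retained participants attend exactly 6 sessions (mean reading) or all reach 6 (share reading). The separate retention target makes the loss visible and limits the effect without removing it. The missing pass share and the unfixed study end are gaps in detail; the conclusion does not depend on them. This should be corrected, but it does not invalidate the study.

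**What to change.** In Aim 1b, make the main figure the share of all participants offered MMPH who complete at least 6 of 8 sessions, counting waitlisted participants only if they receive the program. Specifically:
- Count leavers at the sessions they completed. Treat unknown attendance as not completing, and state how many are unknown.
- Give an exact 95% confidence interval, with the retained-only rate beside it.
- State the share that counts as a pass, and whether study end means week 8 or the end of follow-up.
- Report investigator-initiated removals separately, since Section 22.1 allows them ("Participants may be withdrawn from the research without their consent").
- Date the change. Section 11.1 says enrolment has stopped (Sections 7.2 and 13.1 still describe it as to come), and under Section 21.1 "The research team will meet weekly to review participant data and accrual". If attendance has already been seen, keep the retained-only rate as the pre-specified figure, report both, and label the new one post hoc.

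The cost is a short wording change and one more reported figure. The reported rate may be lower. Some leavers' counts may be incomplete: no section describes logging of the recorded sessions, although the symptom ratings around each module use in Table 1 might give a partial trace. Section 22.3 also lets people who withdraw refuse use of their data ("If the participants do not allow the use of the data, we will make every attempt to destroy the data"). Counting unknowns as not completing is conservative and can bias the rate downward, which is why their number should be shown.

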3.0 Scientific Endpoints*

3.1 *Describe the scientific endpoint(s), the main result or occurrence under study.*

*NOTE: Scientific endpoints are outcomes defined before the study begins to determine whether the objectives of the study have been met and to draw conclusions from the data. Include primary and secondary endpoints. Some example endpoints are: reduction of symptoms, improvement in quality of life, or survival. Your response should **not** be a date.*

Response: Symptom Severity Reduction per PAHSS and HRQOL improvement per EmPHasis-10.

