5.0 Study Design*

5.1 *Describe and explain the study design (e.g. case-control, cross-sectional, ethnographic, experimental, interventional, longitudinal, observational).*

This study will engage community-dwelling URM adults with PH living in the United States. We will use a two-group comparative study design where waitlisted participants will serve as controls. Considering a 20% attrition rate in a behavioral health intervention study, we aim to enroll a total of 20, with at least 16 participants to address study aims (8-10 in each Group).³⁴ As a pilot study, power analysis is not necessary. Statistical analysis will include descriptive statistics, mixed-effect modeling for repeated measures, and within-group and between-groups comparisons using t-tests or Wilcoxon signed-rank test as appropriate and Cohen's d effect size calculation. Multi-time data collection will be done via daily mobile-APP use.

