7.0 Local Number of Subjects

7.1 *Indicate the total number of subjects that will be enrolled or records that will be reviewed locally.*

Response: 20 participants

7.2 *If applicable, indicate how many subjects you expect to screen to reach your target sample (i.e. your screen failure rate).*

Response: Potentially eligible patients from UBMD clinic, URMC, RRH, as well as patients across the US from sources such as Research Match and Facebook will be screened by research team at UB. Potentially eligible and interested PH patients will self-refer and contact us for screening. We will also invited PH patients across the US to participate in the study using additional recruitment sources such as Research Match, across the US CTSA Hub advertisement, and

Social media (Facebook) advertisement. With the approved amendment to include all ethnicity, we will be able to reach the target enrollment goal as planned. Our enrollment goal is 20 patients.

7.3 *Justify the feasibility of recruiting the proposed number of eligible subjects within the anticipated recruitment period. For example, how many potential subjects do you have access to? What percentage of those potential subjects do you need to recruit?*

Response: An enrollment rate to a mind-body intervention is approximately 30%, yielding about 103 participants. Considering a 15% attrition rate, we will enroll 20 participants to achieve at least 8 in each Group. We received verbal agreements from PH specialists at these locations to assist in referring, of eligible participants in the study.

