19.0 Data Management and Analysis*

19.1 Describe the data analysis plan, including any statistical procedures. This section applies to both quantitative and qualitative analysis.

As a pilot study, power analysis is not necessary. Statistical analysis will include descriptive statistics, mixed-effect modeling for repeated measures, and within-group and between-groups comparisons using t-tests or Wilcoxon signed-rank test as appropriate and Cohen's d effect size calculation. Multi-time data collection will be done via daily mobile-APP use.

We will follow the standard procedure in quantitative data analysis that includes general data inspection to verify the accuracy, completeness, and normality of the dataset using the SPSS23 program. We will compare clinical outcomes within-group (pre-post) as well as between groups in the post-intervention period. We will follow the recommendation of inappropriate statistical analysis and interpretation specific to each survey. For continuous variables, we will use a paired student t-test, independent t-test analytical approaches. For categorical variables and non-normally distributed variables, we will use non-parametric statistical methods (X2). Frequency distributions will be produced for all variables, and demographic information will be used to describe the sample. The impact of the M-App use on outcome variables will be analyzed using paired t-test and repeated measure ANOVA.

Qualitative data (focused-group interview data) will be analyzed using the standard qualitative thematic analysis procedure. We will transcribe the audio-recorded data and upload it into NViVo data management system. We will adhere to the thematic analysis method, described as follows:

1. A researcher will read and re-read the entire text to get a general sense of the participants' whole experience of being a student during the COVID-19 pandemic. While reading through the transcript, the researcher will take initial notes and perform a general review to get familiar with the data before analyzing the data.
2. The researcher will descriptively open code by dividing the significant text segments into 'meaningful units', keeping the participants' own words. The researcher will re-read all the codes again to eliminate redundancies.

The comparative discussion of these codes with other research team members to achieve a consensus will provide a validation step.

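### The long-term part of Hypothesis 2 names no comparator, and section 19.1 does not say whether the within-group or the between-group comparison decides Aim 2

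*Combined protocol and SAP*

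**What the plan says.** Section 5.1 sets the design: "We will use a two-group comparative study design where waitlisted participants will serve as controls". The same section plans "Considering a 20% attrition rate in a behavioral health intervention study, we aim to enroll a total of 20, with at least 16 participants", which it gives as 8 to 10 per group.

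The statements of purpose do not mention the control group. Aim 2 in section 2.1 is "To determine the clinical impacts of an MMPH program in PH-symptom, anxiety, and depression reduction". The long-term part of Hypothesis 2 in section 2.2 reads "Participants will report decreases in the prevalence and intensity of PH-related symptoms, depression, and improved quality of life at the end of the MMPH program". Section 3.1 gives the endpoints as "Symptom Severity Reduction per PAHSS and HRQOL improvement per EmPHasis-10".

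The analysis text covers both kinds of comparison. Section 19.1 (and section 5.1 in summary) lists mixed-effects modelling, within-group and between-group tests and Cohen's d. It says that clinical outcomes will be compared pre-post within groups and also between groups after the intervention. It then gives a paired t-test and repeated-measures ANOVA as the analysis of the impact of app use. It does not say which comparison, or which Cohen's d, represents the MMPH effect for Aim 2. It states no significance level, and on power it says "As a pilot study, power analysis is not necessary".

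**The concern.** A waitlist group is there so that change under MMPH can be read against change over the same weeks without it. Section 4.1 describes the earlier in-person programme from which MMPH was adapted as a single-group pilot with pre-post comparisons. The control group is what this trial adds, and the hypothesis does not use it.

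This matters for the PAHSS, EmPHasis-10 and PHQ-9, which a concurrent control can inform. It does not concern the ratings taken before and after each module. The outcomes are participant-reported (section 18.2), participants on a waitlist know that they are waiting, and recruitment includes self-referral and advertising (sections 7.2 and 11.1). Expectation, ongoing PH care or natural fluctuation could move scores in either direction over 8 weeks. If scores improve in both groups alike, the hypothesis as worded is met, and nothing in section 19.1 tells the analyst to draw the opposite conclusion. A pre-post Cohen's d could then be carried forward as the MMPH effect when it also contains whatever change the controls had.

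**Working it through.** **1. The plan's own figure.** To retain 16 after 20% attrition: 16 / (1 − 0.20) = 20, which reproduces the enrolment target. Section 7.3 uses a different rate, "Considering a 15% attrition rate, we will enroll 20 participants to achieve at least 8 in each Group": 16 / 0.85 = 18.8, so 19, and 20 is still enough. The group sizes of 8 to 10 used below are therefore the plan's own.

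**2. What is assumed.** The documents give no SD, pre-post correlation, drift or alpha. For illustration: SD 1 at both times, correlation r of 0.5 or 0.7, two-sided alpha 0.05, no MMPH effect, and the same mean improvement δ of 0, 0.3 or 0.5 SD in both groups.

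**3. Paired test within the MMPH group.** SD of change = √(2(1 − r)), which is 1.000 for r = 0.5 and 0.775 for r = 0.7. The noncentrality is δ√n / SD of change, with n − 1 degrees of freedom. The critical t is 2.365 for n = 8 and 2.262 for n = 10. Example: n = 10, r = 0.7, δ = 0.5 gives 0.5 × 3.162 / 0.775 = 2.04, and the chance of a significant improvement is 0.446.

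| n per group | r | δ = 0 | δ = 0.3 | δ = 0.5 |
|---|---|---|---|---|
| 8 | 0.5 | 0.025 | 0.111 | 0.231 |
| 8 | 0.7 | 0.025 | 0.157 | 0.351 |
| 10 | 0.5 | 0.025 | 0.134 | 0.293 |
| 10 | 0.7 | 0.025 | 0.194 | 0.446 |

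A simulation of 50,000 trials per scenario agrees to within 0.01 (for example 0.443 in the last cell).

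**4. Between-group test on the same data.** Equal drift cancels, so the expected difference is zero. In the simulation the independent t-test on post-intervention scores favoured MMPH in 2.4% to 2.6% of trials in every scenario.

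**5. Precision of the between-group difference in change.** The 95% CI half-width is t(0.975, 2n − 2) × SD of change × √(2/n).
- Widest case, n = 8 and r = 0.5: 2.145 × 1.000 × 0.500 = 1.07 SD.
- Narrowest case, n = 10 and r = 0.7: 2.101 × 0.775 × 0.447 = 0.73 SD.

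An independent t-test reaches 80% power only at a standardised difference of about 1.51 (8 per group) or 1.32 (10 per group). The contrast can be estimated in this pilot but not tested with useful power.

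**The case against.** The strongest reply is that the control comparison is already planned. Sections 5.1 and 19.1 both list between-group tests, and the clinical outcomes that section 19.1 compares are those of Hypothesis 2. That stands. A reader might infer from the hypothesis that the plan ignores its controls, or that pre-post change decides Aim 2 whatever the controls show. The documents do not say either. The gap is that neither comparison is named as decisive.

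Three further readings would go too far.
- Section 3.1 might seem to define success without a control. An endpoint names the outcome, and the response follows the examples printed in the form, so 3.1 is not itself a fault.
- Section 22.3 says "Pre and post comparison of the experimental Group will be conducted as aggregate means using all available data collected", which might be read as making the pre-post comparison the main analysis. That sentence concerns data handling after withdrawal and does not rank the analyses.
- Aim 2 might be read as confirmatory. Section 1.0 speaks of preliminary impacts, and no success rule is set for Aim 2.

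It is also fair to object that no passage supports a drift of 0.3 to 0.5 SD. With no drift the paired test has its nominal 2.5% rate in that direction, and worsening is possible in this disease. Section 8.1 sets no symptom threshold, so eligibility does not by itself create regression to the mean.

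What remains is that the hypothesis has no comparator, and that the one sentence in section 19.1 tying tests to impact names a paired t-test and repeated-measures ANOVA without mentioning group.

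**Conclusion.** The point holds as a gap in wording and linkage between sections 2.2 and 19.1. As worded, the long-term part of Hypothesis 2 is met by a pre-post improvement that the waitlist group shares. Under the assumptions shown, and with no MMPH effect, a significant within-group improvement appears in 2.5% to about 45% of trials, depending mainly on the shared drift. The between-group test favours MMPH in about 2.5%. The range is illustrative, because every input except group size is assumed.

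The issue affects how clinical impact is interpreted, not the sample size. It is worth correcting because naming the decisive comparison is cheap and gives the waitlist group its purpose.

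**What to change.** - **Section 2.2:** word the long-term part of Hypothesis 2 as a greater reduction in PAHSS and PHQ-9 scores and a greater improvement on EmPHasis-10 in MMPH participants than in waitlisted participants over the same 8 weeks.
- **Section 19.1:** state that Aim 2 is interpreted on the between-group difference in change, or the baseline-adjusted difference (choose one), in these three measures. Report it with a 95% CI as a preliminary estimate. Label within-group pre-post change as descriptive.
- **Table 1:** confirm that waitlist scores are collected at the start and end of the same 8 weeks. The table shows only MMPH session weeks and no waitlist schedule. If the scores are collected, no new data are needed. If they are not, rewording alone will not make the contrast computable.
- **Timing:** section 11.1 says that enrolment has ended, so make the change as a dated amendment and disclose it in the report.

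The cost is wording, plus a less flattering result. The interval will be wide (half-width about 0.7 to 1.1 SD under the assumptions above) and may look less favourable than the pre-post change. The documents do not state how participants are allocated to the two groups, so the contrast should be reported with that caveat and not as a clean causal effect.
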